5.2 Planned Enrollment (Aim 2, primary objective)

ANTICIPATED/PLANNED ENROLLMENT for ENTIRE STUDY: Number of Participants (must provide exact numbers. i.e. no range)			
Ethnic Categories	Sex/Gender		
	Females	Males	Total
Hispanic or Latino	0	0	0
Not Hispanic or Latino	5,680	0	5,680
Ethnic Categories: Total of All Participants	5,680	0	5,680
Racial Categories			
American Indian/Alaska Native	0	0	0
Asian	0	0	0
Native Hawaiian or Other Pacific Islander	0	0	0
Black or African American	5,680	0	5,680
White	0	0	0
More Than One Race	0	0	0
Racial Categories: Total of All Participants	5,680	0	5,680

5.3 Analysis Plans

5.3.1 Analysis plan relevant to Aim 1

Focus groups will be audio recorded and both translated and transcribed, using experienced staff from whom we have an established track record of receiving high quality translations. Interview data will be audio recorded and transcribed verbatim. A thematic analysis based on the socially constructivist version of grounded theory will be conducted.³³⁻³⁵ This approach allows for the identification of emergent themes alongside consideration of knowledge from the literature, the SCT constructs (focus groups), and the CFIR domains (interviews). Data analysis will be conducted by a minimum of two members of the research team, including [name], with frequent cross-checking across emergent themes. NVivo12³⁶ software will be used. Any disagreement in themes or coding will be addressed through consensus building. The analysis process will include a rigorous process of the identification and refinement of emergent themes. Uniquely, our research team has always ensured that one of the two coders is a Somali research team member. In our experience, this deepens the process of reviewing emerging themes, and ensures the analytic process thoughtfully considers and integrates perspectives from both a Somali and non-Somali analyst.

5.3.2 Analysis plan relevant to Aim 2

We will use difference-in-difference methods to compare between-period changes in screening completion in women in the intervention and control clinics. Between-period changes in intervention clinic women will be compared with between-period changes in control clinic women over the same time frame to control for secular trends in screening completion that could potentially confound the comparison if it were conducted only in the intervention clinics. Validity of the difference-in-difference approach depends on the reasonable assumption that secular trends equally affect screening uptake in women in both groups of clinics. Our primary outcome analysis will include Somali patients only. A secondary outcome analysis will include all patients.

The 12-month pre-intervention period is February 20, 2022 through February 19, 2023. The 12-month post-intervention period is February 20, 2023 through February 19, 2024. During each period, eligible individuals are identified through the EHR. Including a full 12 months for each pre and post period minimizes the risk of bias from confounding seasonal factors.

The primary outcome of screening completion is defined as either: a) receiving Pap and/or HPV testing by a clinician, or b) self-sampling HPV-negative or HPV16/18+; or c) self-sampling positive for other HR-HPV types or unsatisfactory, and returning for a follow-up Pap test to complete the screening episode. For individuals with other HR-HPV or unsatisfactory test results on self-sampling, a follow-up Pap test is required. Therefore, our criterion specifies that if the Pap test is not completed, the individual will not be considered completely screened. Individuals who initiate screening during the 12-month pre- or post-intervention period are allowed up to 3 months after the screening initiation date to complete the screening episode, if necessary (e.g., returning for a follow-up Pap test after self-sampling positive for other HR-HPV types or unsatisfactory). Analyses will model time to initiating a completed screening episode.

To analyze the data using a difference-in-difference approach, we will fit a Cox proportional hazards model with time to initiating a completed screening episode as the outcome, $\lambda(t \mid X_i, W_i, Z_i) = \lambda(t) \exp\{\beta_1 X_i + \beta_2 W_i + \beta_3 X_i W_i + \beta_4 Z_i + \beta_5 Z_i W_i\}$, where $\lambda(t)$ is the baseline hazard function indexed by time on study in the pre- or post-intervention study period, X_i is an indicator of

pre-intervention ($X_i=0$) or post-intervention ($X_i=1$) cohort, W_i is an indicator of study ($W_i=0$) or control ($W_i=1$) clinic, and Z_i is a vector that includes adjustment for patient covariates, e.g., age, time since last cervical screen. We will use robust standard errors to account for correlation between observations in the pre- and post-intervention cohorts (i.e., women who are due for screening during the pre-intervention period and are seen again in the post-intervention period prior to being screened). A similar model will be used for the secondary outcome of screening initiation, and for the secondary objective these analyses will be applied to the larger cohort of all women (not just Somali-American women).

We will report the proportions completing necessary in-clinic follow-up within 3 months after an abnormal kit result by screening history, and we will summarize the numbers of women that opt for clinician-administered, self-sampling, and no screening in the intervention group (primary: Somali-American women, secondary: all women)

5.3.3 Analysis plan relevant to Aim 3

We will use a mixed methods approach to develop a RE-AIM based analysis³⁸⁻⁴⁰ of clinic and patient perspectives on implementation (see Table 3). We will also draw on SCT and CFIR, as used in Aim 1, to inform the qualitative component of the RE-AIM analysis. First, we will ask patients, administrators, physicians, nurses, interpreters, MAs, and CHWs at each clinic to identify their experience of implementation. We will use these data to identify barriers and facilitators for implementing HPV self-sampling, and needs for ongoing sustainability. Finally, we will use a mixed methods approach to analyze data across each RE-AIM component. Each step of the analysis will be reviewed and refined by the CAB.

The analytical process will happen in two stages. In stage one, the interview data will be translated and transcribed. A thematic analysis will be conducted, following the rigorous process outlined in Aim 1.³³ The resultant thematic analysis will be integrated into stage two. In stage two, a mixed methods approach will be used to consolidate data collected across Aims 1-3. The analysis will be shared with the CAB throughout the analytic process, allowing for extensive input from the CAB, with a particular focus on how to address issues of cervical cancer screening disparities for Somali women.

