3. PATIENT SELECTION

3.1 Inclusion Criteria

3.1.1 Aim 1

Focus groups:

- (a) Identify as a Somali woman
- (b) Between ages of 30-65 years and eligible for cervical cancer screening

Clinic interviews:

- (a) Administrators, physicians, nurses, interpreters, community health workers (CHWs), and medical assistants (MAs), employed at intervention clinics

3.1.2 Aim 2

Primary objective:

- (a) Identify as a Somali woman
- (b) Between ages of 30-65 years
- (c) Due or overdue for routine cervical cancer screening
- (d) Receiving care at intervention clinics (MHealth Fairview Smiley's Family Medicine clinic, Community-University Health Care Center (CUHCC), or People's Center Clinics and Services) or control clinics (across the MHealth Fairview system)

Secondary objective:

- (a) Between ages of 30-65 years
- (b) Due or overdue for routine cervical cancer screening
- (c) Receiving care at intervention clinics (MHealth Fairview Smiley's Family Medicine clinic, Community-University Health Care Center (CUHCC), or People's Center Clinics and Services) or control clinics (across the MHealth Fairview system)

3.1.3 Aim 3

Patient interviews:

- (
 - (a) Between ages of 30-65 years
 - (b) Participated in HPV self-sampling for cervical cancer screening at an intervention clinic

Clinic interviews:

- (a) Administrators, physicians, nurses, interpreters, CHWs, and MAs, employed at intervention clinics

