4.2 Procedures

4.2.1 Study Design

Aim 1

Patient focus groups, and individual provider or clinic staff interviews will be conducted.

Aim 2

Three primary care clinics (M Health Fairview Clinic - Smiley's, Community-University Health Care Center (CUHCC) and People's Center Clinics & Services) will implement HPV self-sampling as part of standard care for cervical cancer screening for all patients.

Programmatically extracted data from these clinics will be compared to cervical cancer screening rates in M Health system clinics that do not implement HPV self-sampling.

Aim 3

Patient 1:1 interviews, and individual provider or clinic staff interviews will be conducted.

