Three primary care clinics (M Health Fairview Clinic - Smiley's, Community-University Health Care Center (CUHCC) and People's Center Clinics & Services) will implement HPV self-sampling as part of standard routine care for cervical cancer screening for all patients, as a new usual care option for cervical cancer screening.

The study team will support the clinics in the implementation process as part of a quality improvement initiative. Findings from Aim 1 will be used to guide the development of the self-sampling components, including refinement of existing self-sampling instructions, the creation of new culturally tailored patient information materials, training materials for providers, workflow guidance, referral processes, and guidance on reporting and communication.

Data collection: Demographics, provider and patient characteristics, healthcare utilization (whether HPV self-sampling offered/completed, questions, or problems patients may have had with HPV self-sampling, screening history, gravidity/parity, receipt of preventative services like mammography or colorectal screening, etc.), health information (e.g. circumcision status, BMI, co-morbidity index, etc.), screening utilization, Pap and HPV test results, coloscopies, biopsy results (to identify CIN 2+ cases), and CIN 2+ treatment will be programmatically extracted from the EHR (in both intervention and control clinics).

Control clinics: All other M Health Fairview primary care clinics in the metro area will be included as control clinics. Control clinics will have passive participation and their only involvement will be that data will be pulled from these clinics from the M Health Fairview research data warehouse.

Aim 3:

We will ask patients who participated in the self-sampling, and administrators, physicians, nurses, interpreters, MAs, and CHWs at each participating clinic, to identify their experience of implementation. We will use these data to identify barriers and facilitators for implementing HPV self-sampling, and needs for ongoing sustainability. Participants who were included in Part 1 can also be included in Aim 3.

Patient interviews (n=30):

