5. STATISTICAL CONSIDERATIONS

5.1 Power Analysis

For our primary outcome analysis (Aim 2), we expect to enroll 1,130 Somali patients in each of the pre- and post-intervention cohorts divided between the three intervention clinics and 4,550 Somali patients in each of the pre- and post-intervention period cohorts in the control clinics. Preliminary data from the two intervention clinics suggests that 15% of Somali patients in the pre-intervention cohort will be screened during the study period, and a somewhat lower screening rate of 11% in the control clinics. Based on results from our prior HOME trial in underscreened women,³⁰ we assume the screening rate in the intervention clinics will increase by at least 9% (from 15% to 24%) in the post-intervention period and will not change in the control clinics. Assuming accrual and screening times are uniformly distributed over the study periods, we estimate 98% power to detect an effect of the intervention in the difference-in-difference analysis. We will still have 80% power if the intervention increases the rate of screening by only 6% (from 15% to 21%). These power calculations are conservative in that they are based on an assumption of independent data, and we expect some overlap between the pre- and post-intervention cohorts in each clinic, and additional intervention clinic (CUHCC). The induced correlation will increase study power since the contrast of interest will be between correlated observations.

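### Aim 2 assigns women to the post-period cohort and to an arm by care received after self-sampling is on offer, with no rule for women seen at both clinic types; movement induced by self-sampling could bias the primary contrast towards benefit

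*Combined protocol and SAP*

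**What the plan says.** Section 3.1.2 makes a woman eligible if she is receiving care at one of the three named intervention clinics or at "control clinics (across the MHealth Fairview system"). It gives no index visit, look-back, usual-clinic or assigned-clinic rule. Section 5.3.2 forms the cohorts separately in each 12-month period: "During each period, eligible individuals are identified through the EHR". The post period starts on 20 February 2023. The Cox model in 5.3.2 carries one 0/1 clinic indicator per observation, and nothing says which value a woman seen at both clinic types receives. The only exclusion listed for Aim 2 (3.2.2) is research opt-out.

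Section 5.3.2 expects women who were due in the pre period and "are seen again in the post-intervention period prior to being screened", and uses robust standard errors for that correlation. It names equal secular trends as the condition for validity and does not mention changes in who makes up each cohort.

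On the controls, 4.2.2 is the specific statement: "All other M Health Fairview primary care clinics in the metro area will be included as control clinics". Smiley's, an intervention clinic, belongs to that same system. Section 4.2.1 describes the comparison as with "cervical cancer screening rates in M Health system clinics that do not implement HPV self-sampling".

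**The concern.** The pre cohort is identified before self-sampling starts, so the intervention cannot influence its membership. The post cohort is identified while the intervention is running, so the intervention can influence both who enters and which arm they enter. A difference-in-difference removes fixed differences between clinic groups and shared trends. It does not remove a change in composition that happens only in the post period and only because of the intervention.

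The harmful case is a woman who would have been screened at a control clinic but goes to an intervention clinic because self-sampling is offered there. She adds a completed screen to the smaller arm and takes one from the larger arm, although no additional woman has been screened. Robust standard errors address correlation between a woman's two records; they do not correct a shift in who is in each arm.

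There is also a plain reproducibility problem. Without a rule for women seen at both clinic types, two analysts could build different primary datasets from the same records.

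**Working it through.** **Inputs (section 5.1).** Intervention arm: "we expect to enroll 1,130 Somali patients in each of the pre- and post-intervention cohorts divided between the three intervention clinics". The control arm is put at 4,550 women per period. Screening: "15% of Somali patients in the pre-intervention cohort will be screened during the study period" in the intervention clinics; for controls the assumed figure is 11%, unchanged between periods. Alpha is not stated; two-sided 0.05 is assumed. The number of movers and the share of them screened are not given, so both are varied.

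**Step 1: reproduce the stated power.** Estimate = ln(post/pre rate, intervention) − ln(post/pre rate, control). SE = √(sum of 1/events over the four cells). Events: 1,130 × 0.15 = 169.5; 1,130 × 0.24 = 271.2; 4,550 × 0.11 = 500.5 in each period.
- 15% to 24%: ln 1.6 = 0.470, SE 0.1165, z = 4.03, power 98.1% (plan: 98%).
- 15% to 21%: 237.3 post events, ln 1.4 = 0.336, SE 0.1188, z = 2.83, power 80.9% (plan: 80%).

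The log rate ratio matches both figures. Replacing each rate p by the cumulative hazard −ln(1−p), which is closer to a Cox hazard ratio, gives 99.4% and 87.9%. Both scales are shown below.

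**Step 2: movers, with no true effect.** Let k control women move in the post period, with a share q screened, each having the result she would have had at the control clinic.
- Post intervention rate = (169.5 + kq)/(1,130 + k)
- Post control rate = (500.5 − kq)/(4,550 − k)

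For k = 45 and q = 1: 214.5/1,175 = 18.3% and 455.5/4,505 = 10.1%. Rate ratio = (0.1826/0.15)/(0.1011/0.11) = 1.32; SE 0.1215; z = 0.281/0.1215 = 2.31; rejection 64%. On the cumulative-hazard scale the ratio is 1.36 and rejection 71%.

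| k | Share screened | Ratio (rate / cumulative hazard) | False rejection |
|---|---|---|---|
| 20 | all | 1.14 / 1.15 | 18% / 21% |
| 30 | all | 1.21 / 1.23 | 35% / 40% |
| 45 | all | 1.32 / 1.36 | 64% / 71% |
| 45 | half | 1.13 / 1.14 | 17% / 19% |
| 45 | 24% | 1.04 / 1.04 | 6% / 6% |
| 45 | 15% | 1.00 / 1.00 | 5% / 5% |

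If movers are instead kept in both cohorts and counted as screened in both, only the intervention cell changes. Then k = 20, 30 and 45 give 1.10 / 1.11, 1.15 / 1.16 and 1.22 / 1.24, with rejection 12% / 13%, 20% / 23% and 37% / 43%.

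A small Cox simulation (120 runs per setting, all movers screened) gave ratios of 1.00, 1.14 and 1.40 and rejection of 5%, 16% and 83% for 0, 20 and 50 movers.

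**Step 3: put k in proportion.** 45/4,550 = 1.0% of control women, but 45/500.5 = 9% of control women who are screened, and 45/214.5 = 21% of post-period intervention screens. On the log-rate scale the expected z reaches 1.96 at 38 movers if all are screened, and at 93 (2.0% of control women) if half are.

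**The case against.** A reader might infer that a handful of women changing clinic would produce a false effect. The documents do not support that. The large figures need dozens of women who move in order to be screened and would have been screened anyway; at k = 45 that is about one in eleven screened control women. Movers who screen at ordinary rates do almost no harm. Movement or dual use that is similar in both periods cancels.

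The documents describe no outreach drawing other clinics' patients in for self-sampling. Section 1.2 speaks of fitting it in with other appointments, and 4.2.2 of a new usual-care option. Covariate adjustment in 5.3.2 includes time since last screen, which may remove part of any bias, though it cannot capture moving in order to be screened. Women drawn in who would otherwise have gone unscreened are a real effect of access, so part of the question is which effect the plan wants to estimate.

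A reader might also infer that the control group is defined in three conflicting ways. That is too strong: 4.2.2 gives a specific definition, and 3.1.2 and 4.2.1 can be read as shorthand for it. The list only needs fixing in time.

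What stands is that arm and post-period entry are set by care received after launch, that no rule covers women seen at both clinic types, and that the plan has no check that would show whether this mattered.

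**Conclusion.** The gap in the rules is certain from the text; the size of any bias is an assumption. The direction is towards benefit when movers would have been screened anyway. At 45 movers the false-rejection rate runs from 6% (24% of movers screened) through 17% to 19% (half) to 64% to 71% (all), assuming no true effect, a two-sided 5% test, independent observations and the cohort sizes and rates in section 5.1. If movers count in both cohorts, the last figure falls to 37% to 43%.

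It would be wrong to conclude that the primary result will be biased, because the documents give no count of movers and nothing about their screening rate. The point calls for a better assignment rule and a check before the result is relied on. It does not undermine the difference-in-difference design.

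**What to change.** In 3.1.2 and 5.3.2:

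1. For each period, assign each woman to the clinic of her last primary care visit in one fixed look-back window ending before 20 February of that period, with the same window length for both periods. Keep that arm wherever she is later seen or screened, so that she counts once per period.
2. Assign women with no visit in the window by their first visit in the period.
3. Pre-specify a sensitivity analysis restricted to women with a visit in the window, entering at the period start whether or not they are seen again. This fixes cohort entry as well as arm, which steps 1 and 2 alone do not.
4. Report, by period, the number of women who changed clinic type or used both.
5. Use the 4.2.2 control list, fixed at the start of the pre period, in all sections.

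For movers with a visit in the window, this returns the null ratio to 1.00 and the error rate to 5%.

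**Cost.** A prior-clinic field and one more model run. Movers who stay in their assigned arm dilute the effect slightly. The sensitivity analysis loses new patients. On the log-rate scale, if 20% are dropped from the post period in both arms, power for 15% to 24% is 97% and for 15% to 21% is 77%. If 20% are dropped from the pre period as well (all four event counts × 0.8, so SE × 1.118), these become 95% and 72%. The 20% is an assumption, and women who enter without being seen again are not counted in it. Section 3.3.2 lists CUHCC and People's Center separately from M Health Fairview, and no record linkage is described. Movement involving those two clinics can be detected only if records can be linked; if they cannot, the plan should state this as a limitation.

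### The primary Cox model has no term for individual clinic, so a change in clinic mix between periods, if it occurs, could be read as an intervention effect

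*Combined protocol and SAP*

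**What the plan says.** Section 5.3.2 writes the primary model out in full. Its terms are period (X), one binary indicator for study or control clinic (W), X×W, covariates Z, and Z×W. There is one baseline hazard, indexed by time on study. Z "is a vector that includes adjustment for patient covariates, e.g., age, time since last cervical screen". Clinic is not named as a covariate, stratum, frailty or cluster. A frailty-model package is in the reference list (reference 37), but the text provided does not cite it.

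On how the cohorts are formed, the same section says: "During each period, eligible individuals are identified through the EHR". Section 5.1 adds that "we expect some overlap between the pre- and post-intervention cohorts in each clinic". On dependence, section 5.3.2 says: "We will use robust standard errors to account for correlation between observations in the pre- and post-intervention cohorts". The explanation that follows concerns women who are due in the first period and seen again, unscreened, in the second.

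The intervention group is three named clinics. For the comparison group, section 4.2.2 says: "All other M Health Fairview primary care clinics in the metro area will be included as control clinics". The validity condition given in section 5.3.2 is that secular trends affect both groups equally. Composition within a group is not discussed.

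**The concern.** A single group indicator removes the average difference between intervention and control clinics. It does not remove fixed differences between clinics inside a group. If every clinic keeps the same share of its group in both periods, this does not matter. The design does not guarantee that, because the cohorts are drawn separately in each period.

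The X×W coefficient is biased by this route only if three things all hold:

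1. Clinics within a group still differ in screening hazard after adjustment for Z and Z×W.
2. Their shares of the group change between periods.
3. The change does not move both groups equally on the log-hazard scale.

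The documents neither show nor exclude any of these. If all three hold, the primary estimate is shifted, upward or downward according to the direction of the mix change. The robust standard errors concern the variance and would leave a shifted estimate where it is. The plan also does not commit to reporting clinic shares by period, so a reader could not tell whether the mix had moved.

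**Working it through.** **Inputs from section 5.1.** Cohort sizes per period of 1,130 (three intervention clinics together) and 4,550 (all control clinics together), with no split by clinic; screening rates of 15% (intervention, pre) and 11% (control, both periods); assumed effects of 15% to 24% and 15% to 21%. No alpha is stated, so two-sided 0.05 is assumed.

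**The plan's own power.** Expected events are 1,130 × 0.15 = 169.5 (intervention, pre), 1,130 × p_post (intervention, post) and 4,550 × 0.11 = 500.5 (control, each period).

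SE = sqrt(1/169.5 + 1/(1,130 × p_post) + 2/500.5); power = Φ(ln(p_post/0.15)/SE − 1.96).

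| p_post | Events | ln(p_post/0.15) | SE | Power | Stated |
|---|---|---|---|---|---|
| 0.24 | 271.2 | 0.470 | 0.1165 | 98.1% | 98% |
| 0.21 | 237.3 | 0.336 | 0.1188 | 80.9% | 80% |

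The stated figures reproduce, so the same standard error can be used to size a mix shift.

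**Illustration of a mix shift.** Everything in this step is assumed: three intervention clinics with one third of the women each before, averaging 15%; controls stable at 11%; no true effect; and a share moving from the lowest-rate to the highest-rate clinic. Then p_post = 0.15 + move × (high − low). The log hazard ratio is taken as ln(p_post/0.15) and as the log ratio of −ln(1 − p). False positives = Φ(logHR/SE − 1.96) + Φ(−logHR/SE − 1.96). The hazard ratio is expressed as intervention relative to control; since W = 1 denotes control, it is exp(−β₃) in the plan's coding.

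| Clinic rates | Move | p_post | SE | HR (rate ratio; −ln(1 − p)) | False positives |
|---|---|---|---|---|---|
| any | 0 | 0.150 | 0.126 | 1.00; 1.00 | 5.0% |
| 13/15/17% | 5 points | 0.152 | 0.125 | 1.013; 1.014 | 5.1%; 5.2% |
| 10/15/20% | 10 points | 0.160 | 0.124 | 1.067; 1.073 | 8.1%; 8.7% |

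**Relative to the planned effects.** On the −ln(1 − p) scale the planned hazard ratios are 0.2744/0.1625 = 1.69 (24% v 15%) and 0.2357/0.1625 = 1.45 (21% v 15%), with logs 0.524 and 0.372. The larger shift has log 0.0703: 0.0703/0.524 = 13% and 0.0703/0.372 = 19% of the planned effects. The smaller has log 0.0144: 3% and 4%.

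**Simulation, pooled v clinic-stratified Cox.** Assumed: 20 control clinics all at 11%, 12 months of follow-up for everyone, no covariates, independent cohorts.

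- Clinics at 10/15/20%, 10-point move, no true effect, 1,168 runs: pooled HR 1.075 with 8.9% rejections; stratified HR 1.00 with 5.1%. The SE of the interaction was 0.1245 pooled and 0.1252 stratified (0.1252/0.1245 = 1.006, or 0.6% larger).
- No shift, true effect 15% to 21%, 1,106 runs: power 85.8% pooled and 86.4% stratified; SE 0.1191 and 0.1192.

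A separate 163-run simulation of the 10/15/20%, 10-point null case agreed: pooled HR 1.07 with 9.8% rejections, stratified HR 1.00 with 4.9%.

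**The case against.** The strongest reply is that no defect is shown. Several design features favour a stable mix: the two 12-month periods are adjacent, the same three clinics form the intervention group throughout, planned cohort sizes are equal, and section 5.1 expects overlap within each clinic. At a 15% screening rate, about 85% of the first cohort stays unscreened and could reappear. If, say, half the second cohort were carried over in the same clinic, a 10-point net shift would need newcomers and leavers to differ by 0.10/0.5 = 20 points in clinic distribution.

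The larger illustration is also demanding. It takes a two-fold range of clinic rates, moves women from exactly the lowest to the highest, and holds the controls still. Since the plan adjusts for Z and Z×W, that range would have to be what remains after adjustment. The covariate list is only illustrative, and section 4.2.2 extracts further patient and provider data that could explain part of any clinic difference. The precision result rests on an assumed number of control clinics and independent cohorts.

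These points stand as arguments about likelihood and size: the bias may well be negligible. They do not supply the missing term. Z is described as patient covariates, and variables such as age and time since last screen remove only the clinic differences they explain. Expected overlap of unstated extent does not fix the shares.

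**Conclusion.** The point holds in its conditional form. The specified model cannot separate a between-period change in clinic mix from the period-by-group effect, and nothing else in the plan guards against that. It is an inexpensive improvement to the primary analysis, not a demonstrated bias.

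The size cannot be determined from the documents. Under the stated assumptions it runs from practically nothing (HR about 1.01) to about 1.07 with false positives of 8.1% to 8.7%. Larger assumed shifts give more, and a shift the other way would hide part of a real effect. The power statement in section 5.1 reproduces and is not challenged.

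**What to change.** 1. In section 5.3.2, stratify the Cox model by clinic, or replace the single W main effect with clinic indicators. W is then absorbed; X, X×W, Z and Z×W stay, as do the robust standard errors for women in both periods.
2. State in advance how each woman is assigned to one clinic per period, by a rule that does not use where the screening took place.
3. Report clinic shares by period and group.

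The cost is a sentence on the model, the attribution rule and one descriptive table. The rule is the real work, because one intervention clinic belongs to the same health system as the controls and women may attend more than one clinic. Some assignment is already needed to define W. The loss of precision was negligible in the simulations. A clinic term removes fixed differences between clinics only; it does not deal with trends that differ from clinic to clinic.
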